### **Abstract**

**Introduction:** Acute pancreatitis represents an acute inflammatory process of the pancreas, which undergoes local and systemic complications, associated with non-negligible morbidity and mortality, and significant economic and quality of life impact. Even after the recovery phase, the development and persistence of sequelae from the inflammatory/necrotic process, including exocrine and endocrine pancreatic insufficiencies, are frequent. Although well documented as consequence of other pancreatic conditions, exocrine pancreatic insufficiency (EPI) after acute pancreatitis is poorly studied and probably underdiagnosed. The prevalence, diagnosis, independent risk factors and therapeutic approaches for EPI after acute pancreatitis need further investigation. Recent evidence suggests the involvement of the pancreas-intestinal axis and immunological dysfunction in several pancreatic pathologies, although their role in the development of EPI after acute pancreatitis is still scarce. Pancreatic enzyme replacement therapy (PERT) is the only treatment currently available in EPI, but the timing for start and duration of this therapy in acute pancreatitis remain to be established.

**Objectives:** Primary objectives: To determine the prevalence, clinical, analytical and nutritional biomarkers and duration of EPI after acute pancreatitis, as well as changes in gut microbiota and immunologic response, and quality of life in EPI and response to PERT after acute pancreatitis. Secondary objectives: To determine the prevalence and biomarkers associated with endocrine pancreatic insufficiency following acute pancreatitis and the presence of gut dysbiosis and immunologic changes in acute pancreatitis according to its severity.

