In clinical practice, there is no a universally easy and reliable test for the diagnosis of EPI. Gold standard diagnosis implies direct tests or 72-hour fecal fat quantification. However, their clinical applicability is limited. Valid alternatives such as fecal elastase-1 and C-labeled mixed triglyceride breath test assessing exocrine pancreatic function have gained special interest and wide use for their availability, cost and ease of application. Based on fecal elastase-1, EPI has been reported at 26.5%, 26.1% and 9.4% for a follow-up of <12months, 12-36months and >36months, respectively. Recent evidence suggests an increasing importance of the pancreas-intestinal axis in pancreatic pathology given the central role of the pancreas in controlling metabolism via its exocrine and endocrine pancreatic functions, possibly due to bacterial metabolites as short-chain fatty acids, immune modulation and pancreatic excretion of antimicrobials. Changes in gut microbiota have been more documented for pancreatic cancer and type 1 diabetes mellitus. Recently, [ZhHeLiCaHuLi19] showed that severe acute pancreatitis can also course with gut dysbiosis by decreased Firmicutes and Bacteroidetes and increased Protobacteria. However, the presence and implications of gut dysbiosis associated with acute pancreatitis and EPI following acute pancreatitis increasing risk of gut-derived infection, remains unclear. In recent years, efforts have been dedicated to find early predictors, alone or in association, of severity, organ dysfunction, and development of complications in patients with acute pancreatitis. In fact, our study group has also been dedicating itself to this thematic, having carried out studies and reflections with publications in international and national journals, identifying C-reactive protein (CRP), red cell distribution width (RDW) and RDW to total serum calcium ratio, as main early predictors (at admission of patients and within the first 24 hours of hospitalization) of severity in acute pancreatitis. However, no single biomarker or score demonstrated high accuracy in early prediction of severity or prognosis of acute pancreatitis to be used in clinical practice and, additionally, there are no studies on early predictors in the development of the EPI complication after acute

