### **B. Objectives**

#### Primary objectives

- To determine the prevalence and duration of EPI following acute pancreatitis, and analytical and nutritional biomarkers related to the development of this complication;
- To evaluate when to start, the efficacy, safety and the duration of PERT in patients with EPI following acute pancreatitis;
- To assess changes in gut microbiota in EPI following acute pancreatitis and response to PERT;
- To assess changes in immunologic response in EPI following acute pancreatitis and response to PERT;
- To assess quality of life in EPI following acute pancreatitis and response to PERT.

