Randomization of patients with EPI following acute pancreatitis for PERT vs placebo. The efficacy, safety and compliance of PERT will be evaluated at 1 (for adjusting PERT dose) and 6 months after PERT start.

Phase 3: Analysis of gut microbiota and assessment of quality of life, and the impact of PERT on clinical and nutritional course, gut dysbiosis and patients' quality of life (at the diagnosis of acute pancreatitis, EPI and after PERT). Evaluation of richness, diversity and uniformity of gut microbiota by DNA sequencing

using the hypervariable region of the 16S rRNA gene. Assessment of quality of life using validated Portuguese versions of SF-36 and QLC-C30-V.3 Assess of PERT impact on clinical and nutritional course, gut dysbiosis and patients' quality of life.

Phase 4: Analysis of immunological changes and the impact of PERT on clinical and nutritional course and immunological status (at the diagnosis of acute pancreatitis, EPI and after PERT). Evaluation of immunological changes through the study of cell populations by flow cytometry (CD4+, CD8+, B-cell, T-cell, natural killer cells, cells ratio) and cytokines, chemokines and growth factors by xMAP/Luminex. Assess PERT impact on clinical and nutritional course and immunological changes.

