#### D.4. Statistical analysis

Using of Statistical Package for the Social Sciences (SPSS) version 25.0 (IL, USA). The statistical significance level will be for a p-value < 0.05. The distribution of data normality will be evaluated by Kolmogorov-Smirnov or Shapiro-Wilk tests. Continuous variables will be expressed as mean and standard deviation or median and interquartile range. Categorical variables will be expressed as frequency and percentage. Univariable analysis will be performed using the Kruskal-Wallis test or Anova test (continuous variables) and Qui-squared test test (categorical variables). The Wilcoxon or Friedman test and the t-Student or Anova test will be used to compare paired data. Cox regression multivariable analysis will be used to determine the independent factors associated with exocrine and endocrine pancreatic insufficiencies. Analysis of PERT efficacy will be performed per-Protocol (PP), excluding loss of follow-up and PERT non-compliance. The temporal evaluation of EPI and PERT response will be evaluated through Kaplan-Meier survival curves. The genome sequences will be grouped in OTU according to their similarity. The alpha taxonomic richness and diversity of stool samples will be expressed in observed species and Shannon index. The composition of fecal microbiota will be expressed in rarefaction curves and comparison of the differences in OTU richness with the t-Welch test. Immunological findings will be expressed by radar charts and representative FACS dot-plots. Additional statistical analysis will be defined a posteriori.

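### The plan tests microbiota composition with rarefaction curves and OTU richness, which do not measure it, so the microbiota objective has no planned test of composition

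*Combined protocol and SAP*

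**What the plan says.** The microbiota analysis occupies three sentences of D.4. Sequences are clustered: "The genome sequences will be grouped in OTU according to their similarity". Within-sample diversity follows: "The alpha taxonomic richness and diversity of stool samples will be expressed in observed species and Shannon index". Composition is then given its own method: "The composition of fecal microbiota will be expressed in rarefaction curves and comparison of the differences in OTU richness with the t-Welch test". The section ends with "Additional statistical analysis will be defined a posteriori".

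The targets are set elsewhere. One of the primary objectives in section B is "To assess changes in gut microbiota in EPI following acute pancreatitis and response to PERT". Phase 3 in D.3 includes "Assess of PERT impact on clinical and nutritional course, gut dysbiosis and patients' quality of life". The secondary objectives in the Abstract include "the presence of gut dysbiosis and immunologic changes in acute pancreatitis according to its severity". As background, the Literature review reports from one cited study that "severe acute pancreatitis can also course with gut dysbiosis by decreased Firmicutes and Bacteroidetes and increased Protobacteria".

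**The concern.** The method named for composition does not measure composition. A rarefaction curve plots the number of OTUs found against the number of reads. Richness is that number at a given depth. Both give the same answer whichever taxa are counted and whichever of them dominate. Observed species is richness again, and the Shannon index uses the set of proportions without regard to which taxon holds which. No between-sample distance, comparison of relative abundance or taxon-level test is named.

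The stake is a primary objective. The planned tests could show no difference between patients with and without EPI, or between PERT and placebo, while the communities differ strongly. If they do show a difference, they cannot say which taxa changed or whether PERT moved them back. An analysis of composition chosen afterwards, among many taxa and distances and with no multiplicity rule, is weak support for a primary objective.

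**Working it through.** **The plan's own figure.** The only computed figure is the sample size in D.3. With 25% prevalence, 10% sampling error and 95% confidence, n = 1.96² × 0.25 × 0.75 / 0.10² = 72.03, rounded up to 73. Half of that is 37 per arm, and 37/0.9 = 41.1, giving 42 per arm and 84 in total. It reproduces, but it is a precision calculation and contains no microbiota effect. It is used here only for the number of completers per arm: 42 × 0.9 = 37.8, about 38.

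**Step 1: what the planned measures depend on.** For taxon proportions p₁, …, p_S:

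- richness = the number of taxa with pᵢ > 0;
- expected rarefaction value at m reads = Σ[1 − (1 − pᵢ)^m];
- Shannon index = −Σ pᵢ ln pᵢ.

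Each is a symmetric sum over taxa. If two taxa exchange their proportions, none of the three changes. This needs no assumption about the data.

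**Step 2: worst-case example (assumed proportions).** Take a = (0.45, 0.35, 0.10, 0.10) and b = (0.10, 0.10, 0.35, 0.45).

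- Richness: 4 in both.
- Shannon: 0.359 + 0.367 + 0.230 + 0.230 = 1.187 in both.
- Bray-Curtis: ½ × (0.35 + 0.25 + 0.25 + 0.35) = 0.60.

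**Step 3: the same worst case as a trial.** Assumptions, none from the documents: 150 OTUs, 5,000 reads, Dirichlet-multinomial counts with concentration 60, 38 per arm. Abundances are exchanged so that a Firmicutes-type group falls from 90% to 24% and a Proteobacteria-type group rises from 1.5% to 68%. Richness is 150 in both arms and Shannon 4.081 in both. The expected rarefaction values are the same (48.9, 122.5 and 148.0 OTUs at 100, 1,000 and 10,000 reads). Bray-Curtis is 0.66. Rejection rates at 0.05 were 5.2% for Welch on richness and 4.9% for Welch on Shannon (1,000 runs), and 100% for PERMANOVA on Bray-Curtis (200 runs).

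**Step 4: a directional shift between phyla.** The change cited in the Literature review is not an exact exchange, so the worst case must not be taken as typical. Assume Firmicutes / Bacteroidetes / Proteobacteria / other start at 50/40/5/5%. The phylum-level Shannon index at the start is 0.50 × 0.693 + 0.40 × 0.916 + 2 × 0.05 × 2.996 = 1.01. The same formulas give:

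| Shift to (%) | Shannon | Change | Bray-Curtis |
|---|---|---|---|
| 40/30/25/5 | 1.22 | +0.21 | 0.20 |
| 30/20/45/5 | 1.19 | +0.18 | 0.40 |
| 20/10/65/5 | 0.98 | −0.03 | 0.60 |

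The largest compositional change gives the smallest change in Shannon. OTU-level Shannon equals phylum-level Shannon plus the share-weighted mean of the within-phylum Shannon values. The changes in the table therefore carry over to OTUs if within-phylum diversity is the same in every phylum.

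A simulation of these shifts (150 OTUs, concentration 20 or 60, 5,000 reads, 38 per group, 500 runs, two assumed allocations of OTUs to phyla) gave these rejection rates for Welch on richness:

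- 40/30/25/5: 5–9% under one allocation, 99–100% under the other;
- 30/20/45/5: 96–100% under both, with Shannon rejecting in 27–99%;
- 20/10/65/5: 100% under one allocation, 4–6% under the other.

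Power thus runs from chance level to 100%, depending on inputs that the documents do not give.

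**The case against.** The strongest reply is that a real dysbiosis seldom leaves richness and evenness untouched, so the planned tests may well detect it. That stands. A reader might infer from Steps 2 and 3 that the planned tests have almost no power against the dysbiosis expected in this trial. The documents do not support that: they give no sizes for the phylum changes and nowhere say that evenness is preserved, and Step 4 shows that power can be high.

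Two further readings also go too far. The primary objective in section B speaks of changes in the microbiota; the word dysbiosis is used in the hypothesis, in Phase 3 and in the Abstract's secondary objectives. And the phylum shift in the Literature review is a finding from one study in severe disease, not the plan's definition of dysbiosis.

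Phase 3 also lists richness, diversity and evenness as its sequencing measures. Observed species and Shannon serve the first two properly and the third in part. The mismatch lies in what D.4 assigns to composition.

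Finally, an OTU table will exist, D.4's general tests for continuous variables could be applied to taxon shares, and further analysis is allowed afterwards. The data would not be lost. But D.4 names no taxon share as a variable, so any such analysis would be chosen after the data are seen.

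**Conclusion.** The point holds. D.4 names a method that does not measure the quantity it is assigned to, and no other planned measure fills the gap. The invariance in Step 1 is exact and rests on no assumption. The size of the loss is not fixed: power is at chance level for a pure exchange of abundance, and otherwise anywhere up to near 100%, depending on the assumed phylum shares, the allocation of OTUs to phyla and the between-patient variation. The supportable statement is that power against a compositional change is not assured, not that it is absent. Whatever the power, a significant richness or Shannon result would not identify the taxa that changed or show reversal under PERT. Because a primary objective is affected and the remedy is cheap, the plan should be corrected before the sequencing data are analysed.

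**What to change.** In D.4:

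1. Relabel the present sentence. Rarefaction curves check sequencing depth, and the Welch test compares OTU richness.
2. Pre-specify a between-sample test of composition, for example PERMANOVA on Bray-Curtis distance with a check of dispersion, for EPI versus no EPI, for the severity groups, and for PERT versus placebo at 6 months.
3. Add a within-patient version for the samples taken before and after PERT or placebo, for example with permutations restricted within patient.
4. Pre-specify taxon-level tests, starting with the three phyla named in the Literature review and then other taxa, with false discovery rate control (for example Benjamini-Hochberg at 5%). Centred log-ratio abundance is one suitable scale.

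Other distances and taxon-level methods would also serve; what matters is that the choice is fixed in advance. The cost is a little more analysis of the same sequencing data, and probably software other than the SPSS version named in D.4. No new samples are needed.

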#### D.5. Ethical aspects

The project will be subject to the standards of good clinical practice and will at all times comply with the ethical precepts in the World Medical Association Helsinki's Declaration and updates, including the Oviedo agreement. This study was approved by Ethical Committee of University of Coimbra (Ref n.º CE-169/2019). Written informed consent will be obtained from all patients. The confidentiality of the data will be respected at all times, by means of the anonymity of the data in the database, in accordance with the General Data Protection (UE 2016/679) and updates.

